9.6. Data Management

All analyses will be carried out under the direction of biostatisticians of CorEvitas.

9.7. Data Analysis

Detailed methodology for summary and statistical analyses of data collected in this study will be documented in a statistical analysis plan (SAP), which will be dated, filed and maintained by the sponsor. The SAP may modify the plans outlined in the protocol; any major modifications of endpoint definitions or their analyses would be reflected in a protocol amendment.

In general, the data for all continuous endpoints will be summarized by timepoint and treatment group in tables containing descriptive statistics (N, mean, standard deviation, standard error of the mean, minimum, 1st, 2nd (ie, median) and 3rd quartiles and maximum) for baseline and change from baseline/percent change from baseline for those endpoints measured at baseline. The data for all categorical endpoints will be summarized by contingency tables that show the counts/frequency in the various categories by treatment group at each timepoint.

For binary endpoints, 95% CI using normal approximation to binomial proportions will be provided for each group. The 95% CI will also be provided for comparisons between groups using normal approximation for the difference in binomial proportions.

Continuous endpoints (eg, HAQ-DI) at month 6 will be analyzed as change from baseline with an analysis of covariance (ANCOVA) model that includes treatment and baseline value as covariates. Comparisons between groups will be performed using 95% CI.

9.8. Quality Control

CorEvitas or its designee monitors the conduct of the registry at each investigative site. Monitoring is primarily conducted remotely. Onsite monitoring visits are conducted once every 3 years, as needed, or as requested. A review of registry records including, but not limited to, the informed consent forms, Questionnaires, original source documents such as supporting medical records and office notes, patient study files, and any other registry documentation is conducted in accordance with applicable regulatory guidelines and the protocol. CorEvitas and its designees are required to maintain the confidentiality of all patients during and after an on-site monitoring visit.

Quality control checks are built into the on-screen data entry systems in an attempt to reduce queries and provide immediate feedback to the investigator regarding inadvertent omissions and out of range or noncompliant values. Changes made at any time are recorded in an audit trail that includes the date, time, and electronic ID of the person making the change.

CorEvitas will address and resolve discrepancies by requesting clarifications and/or missing data from the investigator as needed. Each investigator is expected to designate a point of contact to address such inquiries and to promptly address and resolve issues. Representatives or designees from CorEvitas reserve the right to perform random or systematic audits of CorEvitas Questionnaires at an investigator's site in order to assess the accuracy of the reported data compared to the information contained in the original medical records.

9.9. Limitations of the Research Methods

The CorEvitas PsA/SpA Registry includes a sample of adult patients with PsA that are not necessarily representative of all adults with PsA in the US. In particular, these are PsA patients with regularly-scheduled visits with rheumatologists. Patients are recruited by rheumatologists who are required to indicate diagnosis upon enrollment of the patient into the CorEvitas PsA/SpA Registry. In addition, history of medication use prior to enrollment is derived from what is reported by patients and their current rheumatologist within the registry. Since registry reporting is not based on a fixed visit schedule, exact timing of visits to fit 6, 12, 24, or 36 months of post index data is not available for all patients so windows of time are used to determine eligible visits. The “cause” of visits is not captured, although the assumption can likely be made that the rheumatologist visit is “PsA-related.” The registry captures provider reported prescribing; there are no measures of patient adherence.

As this is a real-world study, missing data could be expected for demographic characteristics (eg, age, etc.); however, the number of patients with missing data is expected to be very small. With multiple time points, some visits may have missing DAPSA (

9.10. Other Aspects

Not applicable.

10. PROTECTION OF HUMAN SUBJECTS

10.1. Patient Information

This study involves data that exist in anonymized structured format and contain no patient personal information.

10.2. Patient Consent

As this study involves anonymized structured data, which according to applicable legal requirements do not contain data subject to privacy laws, obtaining informed consent from patients by Pfizer is not required.

10.3. Institutional Review Board (IRB)/Independent Ethics Committee (IEC)

This database does not contain any patient identification information (eg, name) and is exempt from IRB review.

10.4. Ethical Conduct of the Study

The study will be conducted in accordance with legal and regulatory requirements, as well as with scientific purpose, value and rigor and follow generally accepted research practices described in CT24-WI-GL02-RF02.

11. MANAGEMENT AND REPORTING OF ADVERSE EVENTS/ADVERSE REACTIONS

This study involves data that exist as structured data by the time of study start. In these data sources, individual patient data are not retrieved or validated, and it is not possible to link (ie, identify a potential association between) a particular product and medical event for any individual. Thus, the minimum criteria for reporting an adverse event (AE) (ie, identifiable patient, identifiable reporter, a suspect product, and event) cannot be met.

12. PLANS FOR DISSEMINATING AND COMMUNICATING STUDY RESULTS

For all publications relating to the study, Pfizer will comply with recognized ethical standards concerning publications and authorship, including Section II - "Ethical Considerations in the Conduct and Reporting of Research" of the Uniform Requirements for Manuscripts Submitted to Biomedical Journals, <http://www.icmje.org/index.html#authorship>, established by the International Committee of Medical Journal Editors.

In the event of any prohibition or restriction imposed (eg, clinical hold) by an applicable competent authority in any area of the world, or if the Corevitae is aware of any new information which might influence the evaluation of the benefits and risks of a Pfizer product, Pfizer should be informed immediately.

14. LIST OF TABLES

Table shells are included in the SAP.

15. LIST OF FIGURES

Figures are included in the SAP.

ANNEX 1. LIST OF STAND ALONE DOCUMENTS

Number	Date	Title
1	20 August 2021	Analysis of tofacitinib initiators with PsA SAP

**Title: Analysis of tofacitinib initiators with PsA**

**Overall Aim:** To describe baseline demographic, therapy history, and disease activity characteristics and assess change in disease activity measures six months after initiation of tofacitinib

To accomplish the overall aim, we will:

**Objective 1:** Summarize patient characteristics at baseline and calculate changes in various disease activity measures over time among all eligible initiators of tofacitinib

**Objective 2:** Summarize patient characteristics at baseline and calculate changes in various disease activity measures separately for monotherapy and combination therapy initiators, and compare these groups

**Definitions:**

- Oral small molecules (OSMs): methotrexate, leflunomide, sulfasalazine, apremilast
- Tofacitinib monotherapy: initiation of tofacitinib with no other (pre-existing or new) DMARD prescriptions
- Tofacitinib combination therapy: initiation of tofacitinib with a concomitant (pre-existing or new) prescription of at least one OSM

**Registry description:**

CorEvitas' Psoriatic Arthritis/Spondyloarthropathy Registry is a prospective, multicenter, observational disease-based registry that was started March 2013.

From initiation until April 2017, inclusion criteria in the registry were as follows:

- Meet diagnostic criteria for psoriatic arthritis (PsA), ankylosing spondylitis (AS), axial or peripheral SpA
- Age  $\geq$  18 years of age as of the patient's PsA/SpA diagnosis
- Subject must be able and willing to provide consent

From April 2017 until February 2018, the inclusion criteria were modified as follows:

- Meet diagnostic criteria for ankylosing spondylitis (AS), axial or peripheral SpA or PsA
- Age  $\geq$  18 years of age as of the patient's PsA/SpA diagnosis
- Subjects needed to be diagnosed with psoriatic arthritis (PsA) by their rheumatologist or meet the modified New York classification criteria for ankylosing spondylitis (AS)
- Subjects needed to be a newly prescribed (first time) user of an FDA-approved eligible biologic for the treatment of PsA or AS at time of enrollment. Eligible biologics for inclusion in the registry include abatacept, adalimumab, certolizumab, etanercept, golimumab, infliximab, secukinumab, ustekinumab (only FDA approved for PsA).

From February 2018 until October 2018, the inclusion criteria were modified as follows:

- Non-biologic medications have been added as eligible medications for enrollment of patients diagnosed with Psoriatic Arthritis.
- Eligibility for Psoriatic Arthritis patients has been expanded to include patients currently on an eligible medication at the time of enrollment.

From October 2018 until August 2019, the enrollment criteria were modified as follows:

- For PsA patients, only incident users (either prescribed or actually receiving first dose on the day of the enrollment visit) of eligible medications are eligible. Patients who are prevalent users (currently receiving a medication or first dose received prior to the enrollment visit) are no longer eligible for new enrollment.
- 1:2 enrollment ratio is defined as one (1) IL-17 inhibitor or JAK-inhibitor to every two (2) biologics.

From August 2019 forward, the enrollment criteria were expanded as follows:

- Apremilast (Otezla) has been added as an eligible medication at enrollment.
- Eligible diagnoses at enrollment will now include PsA, AS (per modNY), or Axial Spondyloarthritis (per ASAS), radiographic or non-radiographic.

CorEvitas patients and their rheumatologists complete questionnaires, including information on laboratory measurements and radiographic results from routine visits, at approximately 6-month intervals.

#### **Study Cohort:**

For this analysis, the eligible population will be selected using the following criteria:

- Have a diagnosis of PsA
- Initiate tofacitinib monotherapy or in combination with OSMs (pre-existing or concurrent) during or after December 2017
- Have a follow-up visit occurring six ( $\pm 3$ ) months after initiation

Initiators will be ineligible for analysis if:

Any initiations result in a combination of tofacitinib with TNFi or non-TNFi bDMARDs, whether multiple initiations occur at the same time or a new therapy is added to an existing regimen

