9.2.2. Exclusion Criteria

Patients meeting any of the following criteria will not be included in the study:

1. Patients taking tofacitinib in combination with any other bDMARD

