### Milestone 2:

The analyses stratified by mono- and combination therapy for this milestone will be completed when the sample reaches at least 100 initiators in both mono- and combination therapy groups.

Consider the demographic, patient, and disease characteristics of the tofacitinib monotherapy and combination therapy initiators in **Table 4**. Categorical variables will be examined using frequencies and proportions, and, when sample size allows for significance testing, differences across therapy patterns will be tested using chi-square or Fisher exact tests. Continuous variables will be summarized using descriptive statistics (n, mean, standard deviation, minimum, 25% percentile, median, 75% percentile, maximum). When sample size allows for significance testing, differences across therapy groups will be tested using Wilcoxon rank sum tests.

In **Table 5**, we will present the therapy status of initiators at the six-month follow-up visit.

**Table 6** will examine the outcomes of interest at the six-month follow-up visit. The change from baseline to six months in continuous outcomes will be analyzed using an analysis of covariance model with fixed effects for treatment group and baseline value. For continuous outcomes, we will not impute missing values. Also, for those discontinuing therapy prior to follow-up, we will use the value immediately prior to discontinuation as the follow-up value. We will present LS Means (standard error) for each therapy group as well as the difference in the LS Means (standard error), 95% CI and p-value. Binary outcomes will be presented as response rates with 95% CIs using normal approximation to binomial proportions. We will provide comparisons of response rates between groups with 95% CIs and p-values using normal approximation for the difference in binomial proportions. As a supportive analysis, treatment difference between the groups will be assessed using logistic regression models with treatment group as the sole covariate. For binary outcomes, we will impute non-response for missing values and for those patients discontinuing therapy prior to follow-up.

In **Table 7**, we will present summary statistics (n, mean (SD), [P0,P25,P50,P75,P100]) for continuous outcomes featured in Table 3 at baseline, six months, and the difference from baseline to six months overall and by therapy group.

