**Table 5. Therapy status six months post-initiation**

	Overall	Mono	Combo	p -value a
All Patients, N				
Remain on tofacitinib, n (%)				
Discontinued tofacitinib, n (%) b				
Switched to a bDMARD, n (%) c				
Added OSM, n (%)				
Discontinued OSM, n (%)				

a p-value from chi-square testb This group consists of those discontinuing tofacitinib and not initiating a bDMARD at or prior to the six-month follow-up visitc This group consists of those discontinuing tofacitinib and initiating a bDMARD at or prior to the six-month follow-up visit

**Table 6.** Disease activity outcomes at six months

	Mono	Combo	Mono vs Combo		
	Binary Outcomes	Response Rate (95% CI) a	Response Rate (95% CI) a	Rate Difference (95% CI) a	p-value a
Achievement of:					
LDA (cDAPSA)					
Minimal Disease Activity					
Body Surface Area Score of 0					
PASDAS < 3.2					
Resolution of enthesitis					
Resolution of dactylitis					
Clinical Global Assessment of PsO – Clear or Almost Clear					
Continuous Outcomes		LS Means (SE)	LS Means (SE)	Δ LS Means (SE) 95% CI	
Baseline to six-month change in:					
cDAPSA					
DAPSA					
PASDAS					
HAQ-DI					
BSA					
CDAI					
Tender joint count					
Swollen joint count					
Patient global skin assessment					
Patient pain					
Patient fatigue					
Clinical Global Assessment of PsO					
Work Time Missed					
Impairment While Working					
Overall Work Impairment					
Activity Impairment					

a 95% CI for the response rate and 95% CI and p-value for the rate difference were based on normal approximation to binomial proportions. OR (95% CI) was based on a logistic regression model with treatment group as the sole covariate

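### The bDMARD exclusion is not tied to the tofacitinib index date, so a bDMARD added to continuing tofacitinib either removes the patient after baseline or has no handling rule

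*SAP*

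**What the plan says.** The SAP (Study Cohort) makes initiators ineligible if "Any initiations result in a combination of tofacitinib with TNFi or non-TNFi bDMARDs", and extends this to cases "whether multiple initiations occur at the same time or a new therapy is added to an existing regimen". It does not say which drug is the new one, or whether the test is applied only when tofacitinib starts. Protocol 9.2.2 excludes "Patients taking tofacitinib in combination with any other bDMARD", again with no time reference.

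The treatment groups, by contrast, are fixed at the start: monotherapy is "initiation of tofacitinib with no other (pre-existing or new) DMARD prescriptions" (SAP, Definitions).

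For outcomes, SAP Milestone 2 gives two rules. For binary endpoints, "we will impute non-response for missing values and for those patients discontinuing therapy prior to follow-up". For continuous endpoints, "for those discontinuing therapy prior to follow-up, we will use the value immediately prior to discontinuation as the follow-up value". Milestone 1, which covers Table 3, states neither.

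For therapy status, Tables 2 and 5 have a row for patients still on tofacitinib, one for those who stopped without a bDMARD, and one for switchers, defined thus: "This group consists of those discontinuing tofacitinib and initiating a bDMARD at or prior to the six-month follow-up visit". Table 5 also has rows for an OSM added or stopped. Neither table has a row for a bDMARD added to tofacitinib.

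**The concern.** Membership of an initiator cohort should be settled by what is known on the index date. Suppose a patient starts tofacitinib alone and has a bDMARD added at month 3. By then tofacitinib is the existing regimen and the bDMARD is the new therapy, so the literal wording makes the patient ineligible. The reason for removal is a post-baseline event that plausibly reflects an inadequate response. A similar patient who stops tofacitinib when starting the same bDMARD stays in the denominator as a non-responder.

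If the rule was meant for the index date only, the add-on patient stays in, but nothing says how the outcome is to be handled. A result obtained on two drugs is then credited to tofacitinib.

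At stake are the six-month response rates, which serve both primary objectives. The mono-versus-combination comparison is also exposed if add-ons are more common in one group. Two analysts could also build different cohorts from the same data.

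**Working it through.** The plan gives no figure on this point, so there is nothing to reproduce. The check is to trace patients through the rules and then to size the effect under stated assumptions.

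**Tracing the rules** (events before the six-month visit):

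| Patient | In cohort? | Row in Tables 2 and 5 | Binary outcome in Table 6 |
|---|---|---|---|
| Stops tofacitinib, no bDMARD | Yes | Discontinued | Non-response |
| Stops tofacitinib, starts a bDMARD | Yes | Switched | Non-response |
| Continues tofacitinib, adds a bDMARD, any-time reading | No | None | None |
| Continues tofacitinib, adds a bDMARD, index-only reading | Yes | Still on tofacitinib (the discontinued and switched rows both need tofacitinib to stop) | As observed on both drugs; non-response only if missing |

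Only the last two rows are a problem. For continuous outcomes under the index-only reading, the carry-back to the value before discontinuation does not apply either, so the value on both drugs is used.

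**Size.** Inputs:
- N = 73 per group, the lower of the two figures printed in protocol 9.5.
- a = number of add-ons, assumed 1 to 7 (about 1% to 10% of 73). The documents give no count.
- p = response rate in the other patients, assumed 20% to 40%.
- q = share of add-on patients who meet the endpoint on both drugs, unknown, from 0 to 1.

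Response rate under each handling:
- add-ons as non-responders: p(N − a)/N
- add-ons excluded: p, which is higher by pa/N
- add-ons kept as observed: [p(N − a) + qa]/N, which is higher by qa/N

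Example with a = 7 and p = 40%: as non-responders, 0.4 × 66/73 = 36.2%. Excluded, 40.0%, higher by 0.4 × 7/73 = 3.8 points. Kept with all seven meeting the endpoint, (26.4 + 7)/73 = 45.8%, higher by 7/73 = 9.6 points.

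Percentage points above counting add-ons as non-responders, N = 73:

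| Add-ons | Excluded (p = 20% to 40%) | Kept, q = 0 | Kept, q = p | Kept, q = 1 |
|---|---|---|---|---|
| 1 | 0.3 to 0.5 | 0 | 0.3 to 0.5 | 1.4 |
| 2 | 0.5 to 1.1 | 0 | 0.5 to 1.1 | 2.7 |
| 4 | 1.1 to 2.2 | 0 | 1.1 to 2.2 | 5.5 |
| 7 | 1.9 to 3.8 | 0 | 1.9 to 3.8 | 9.6 |

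For the whole cohort, the SAP feasibility table gives 59 + 55 = 114 patients with a six-month visit. With 1 to 11 add-ons, the same formulas give 0.2 to 3.9 points for exclusion and 0 to 9.6 points for keeping observed outcomes.

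**Retention.** Add-on patients are still taking tofacitinib. Removing them takes the same number from numerator and denominator, which lowers the retained share. With assumed counts, 50/73 = 68.5% becomes 47/70 = 67.1% after removing three.

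**The case against.** The best reply is that the rule was always meant for the index date. It sits directly below an inclusion criterion that covers OSMs already in use or started alongside tofacitinib, and the exclusion can be read as mirroring that pair: simultaneous starts, or tofacitinib added to a bDMARD already in use. The group definitions are tied to initiation. The feasibility table counts 213 eligible initiations (132 + 81) before the six-month visit is applied. This makes the index-only reading plausible, but the text does not say so, and that reading still leaves the add-on patient without a handling rule.

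A second reply is that such patients are rare. Protocol section 7 describes approval alongside nonbiologic DMARDs, which fits that view. With one or two add-ons per group the effect is about 0 to 3 points, against a planned half-width of under 11 points (protocol 9.5). This limits the size. It does not remove the defect, because a confidence interval does not allow for bias.

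A third reply is that non-response is one choice of estimand, and that observed outcomes are defensible in a descriptive study. That is fair. The case for non-response as the main rule is consistency with switchers, and observed outcomes belong in a sensitivity analysis.

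A reader might also infer several stronger things that the documents do not support:
- That an add-on patient automatically becomes a responder. This happens only if the endpoint is met, and a missing value is set to non-response in Table 6.
- That treatment failures in general are lost. Those who stop tofacitinib before the visit, switchers included, are kept and set to non-response.
- That response is raised on either reading. Under the index-only reading the effect is zero if no add-on patient meets the endpoint.
- That retention is inflated. These patients do remain on tofacitinib, and removing them lowers the retained share.

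**Conclusion.** The point holds, limited to a bDMARD added to continuing tofacitinib before the six-month visit. The exclusion lacks an index-date anchor in both documents. Followed literally, it conditions the cohort on a post-baseline event and treats add-ons and switchers in opposite ways. Read as index-only, it leaves add-ons among those still on tofacitinib, with the two-drug outcome taken as it stands.

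The upward shift in response rate is about 0.3 to 3.8 points if add-ons are excluded and 0 to at most 9.6 points if they are kept as observed. Both are measured against counting add-ons as non-responders. They rest on an assumed 1 to 7 add-ons among 73 and 20–40% response in the rest, and the true number is probably at the low end. A bias in mono versus combination needs add-on rates that differ by group, for which the documents have no data. The point merits correction because the remedy is specific and cheap, not because the effect is shown to be large.

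**What to change.** 1. In SAP Study Cohort and protocol 9.2.2, state in the same words that the exclusion applies only to a bDMARD being taken or started on the tofacitinib index date.
2. Keep patients who add a bDMARD later. In the binary analyses (Table 6, and Table 3 where no rule is given) count those who add one before the six-month visit as non-responders, in line with switchers, and report observed outcomes as a sensitivity analysis.
3. State which value these patients contribute to the continuous outcomes, since the present rule covers only discontinuers.
4. Add a row for an added bDMARD to Tables 2 and 5, by group in Table 5, so that the frequency is visible.

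If the sponsor does intend the any-time exclusion, the SAP should say so and report the number removed in each group.

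The cost is a wording change in two documents, one table row and one sensitivity analysis. No new data should be needed: protocol 9.4 says that the start of a new eligible drug, biologics included, prompts registry questionnaires. The downside is that response rates may come out slightly less favourable.
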